## 8. Study Assessments and Procedures

Unless otherwise stated, study assessments will be performed according to hVIVO SOPs.

Study procedures and their timing are summarised in the SoA (Section 1.2). Protocol waivers or exemptions are not allowed. Adherence to the study design requirements, including those specified in the SoA, is essential and required for study conduct. Immediate safety concerns should be discussed with the Sponsor upon occurrence or awareness to determine if the participant should continue or discontinue study intervention.

All screening evaluations must be completed and reviewed to confirm that potential participants meet all eligibility criteria. The Investigator will maintain a screening log to record details of all participants screened and to document eligibility or record the reasons for screening failure, as applicable.

For all study assessments, the nearest value obtained prior to dosing will be used as the baseline measure for assessments, unless stated otherwise.

Procedures conducted as part of the hVIVO Generic Screening process and obtained before signing of the study specific ICF may be utilised for screening or baseline purposes provided the procedures met the protocol-specified criteria and were performed within the time frame defined in the SoA.

Where applicable, unless otherwise stated, normal ranges will be identified in the Investigator Trial Master File (TMF).

• The maximum amount of blood collected from each participant over the duration of the study, including any extra assessments that may be required, will not exceed 550 mL for any given 8-week period. Repeat or unscheduled samples may be taken for safety reasons or for technical issues with the samples.

# 8.1. Medical and Medication History

Medical and medication histories including any allergies will be recorded at screening and on Day -2 / -1, including, but not limited to, detailed histories on allergies (e.g., rhinitis, dermatitis, food, aspirin / non-steroidal anti-inflammatory drugs and asthma).

## 8.2. Demographics

Demographic data will be recorded at screening.

# 8.3. Height, Weight and Body Mass Index

Height and weight measurements will be recorded in compliance with hVIVO's standard procedures.

BMI will be calculated as: BMI  $(kg/m^2) = Weight (kg)$ Height  $(m)^2$ 

# 8.4. Alcohol Breath Testing

Alcohol breath testing will be conducted to determine compliance with the study alcohol restrictions. Additional tests may be conducted for assessing eligibility at the discretion of the Investigator. Results will be recorded in the source documents.

# 8.5. Urine Samples and Assessments

#### 8.5.1. Urinalysis

Clinical urine safety analysis will be undertaken using commercially available urine test strips that provide an instant result that will be documented in the source data.

Urinalysis will be performed to evaluate the parameters described in Appendix 2.

If the dipstick yields abnormal results, a urine sample may be sent for microscopy, culture, and sensitivity (MCS), at the Investigator's discretion. MCS will include but is not limited to RBC, WBC, epithelial cells, crystals, casts, and bacteria.

Urine safety analysis values will be evaluated by the Investigator for clinical relevance. Those deemed to be clinically significant will be reported as AEs.

#### 8.5.2. Drugs of Abuse

Urinalysis will be performed for drugs of abuse and cotinine using commercially available kits that provide an instant result, which will be documented in the source data.

Drugs of abuse screen will include (but is not limited to) amphetamines, barbiturates, cocaine, opiates, cannabinoids, and benzodiazepines.

#### 8.5.3. Pregnancy Test

Female participants of childbearing potential are to have a urine pregnancy test at screening. Participants will only be enrolled if the pregnancy test is negative.

Note: Pregnancy test must be performed even if the participant is menstruating at the time of the study visit.

All female participants will have a serum sample tested for  $\beta$ -human chorionic gonadotrophin ( $\beta$ -hCG) on admission to quarantine.

Blood samples will be tested for serum FSH in post-menopausal female participants only.

## 8.6. Complete Physical Examination

A complete physical examination to include a full systemic assessment.

# 8.7. Directed Physical Examination

Directed physical examinations will be conducted as deemed appropriate by the Investigator and will include examination of the ears, nose, throat, and chest (via stethoscope).

Assessment and grading of any upper respiratory tract (URT) (nasal discharge, otitis, pharyngitis, sinus tenderness) and LRT symptoms (abnormal breath sounds externally [e.g., stridor] and on chest auscultation [wheezing or rhonchi, crepitations] will be performed. Physician-reported assessments of viral challenge related illness will be graded in accordance with their intensity and documented in the source data.

Following viral challenge, URT and LRT symptoms (as described above) will be expected and presumed to represent virus infection consequent to viral challenge and will not be additionally captured as AEs unless they meet the definition of an AE and are deemed to be clinically significant (in the opinion of the Investigator) to be classed as AEs.

Following viral challenge all unexpected (in the opinion of the Investigator) directed physical examination findings will be captured as AEs, along with all other occurrences that meet the criteria for an AE.

## 8.8. Vital Signs

Vital signs assessments will be recorded as follows:

- Heart rate (HR) will be recorded in beats per minute.
- Respiratory rate (RR): respirations will be counted and recorded as breaths per minute.
- Blood pressure (BP): systolic BP and diastolic BP will be measured in millimetres of mercury (mmHg); measurements will be made supine. Where possible, the same arm will be used for all measurements.
- Peripheral arterial oxygen saturation (SpO2%) will be assessed using pulse oximetry.

In the event of a participant having an unexpected abnormal or out of normal range result, the assessment may be repeated after at least 2 minutes to exclude a technical fault and confirm the original reading. The assessment may then be repeated at the PI's discretion and in accordance with hVIVO's SOPs.

Study specific normal ranges are provided in Appendix 4. If a result is out of the normal range and meets the criteria for an AE, the severity of the AE will be guided by the Division of Microbiology and Infectious Diseases (DMID) Adult Toxicity Table November 2007.

Deterioration in a vital sign (compared to baseline) should only be reported as an AE if the deterioration fulfils the criteria for an AE. If deterioration in a vital sign is associated with clinical signs and symptoms, the sign or symptom will be reported as an AE and the associated vital sign will be considered as additional information.

# 8.9. Tympanic Temperature

The study specific normal range for tympanic temperature is detailed in Appendix 4. The severity of out of normal range values will be assigned using the DMID toxicity scale as a guide.

Temperature may be more frequently monitored in quarantine if appropriate.

Following viral challenge, pyrexia will be expected and presumed to represent virus infection consequent to viral challenge and will not be additionally captured as an AE unless it meets the definition of an AE and is deemed to be clinically significant (in the opinion of the Investigator) to be classed as an AE.

Following viral challenge all unexpected (in the opinion of the Investigator) pyrexia will be captured as an AE, along with all other occurrences that meet the criteria for an AE.

Febrile illness is defined as any occurrence of temperature ≥37.9°C.

# 8.10. Exploratory Wearables and Continuous Monitoring

Participants may be given the option to take part in a separate ethically approved exploratory non-interventional trial that aims to collect physiological data via a wearable device. Participants will have the wearable device trial explained to them and a choice to opt into the trial, which will require them to consent to wear a wearable device (such as a wrist-or armband during the challenge trial, via an additional informed consent, which will be separately ethically approved). There will be no impact on participants eligibility and/or safety follow-up or treatment in the challenge trial. The wearable device will not replace any conventional safety monitoring. All participants will be monitored for AEs related to the wearable device from signing of the wearable device ICF to the end of data capture. An AE related to the wearable device may lead to discontinuation of the exploratory wearable study, without having an impact on the human challenge trial.

# 8.11. Participant Diary Cards

#### Symptom Diary Card (Categorical and Visual Analogue Scale)

Participants will report and assess the severity of any Challenge virus-related symptoms using the hVIVO symptom diary card. This information will be collected using a paper form.

The following symptoms in the 13-item symptom questionnaire will be graded on a scale of 0-3 (Grade 0: No symptoms; Grade 1: just noticeable; Grade 2: clearly bothersome from time to time but does not interfere with me doing my normal daily activities; Grade 3: Quite bothersome most or all the time, and it stops me participating in activities: Shortness of Breath and Wheeze have an additional Grade 4: Symptoms at rest:

- Runny nose
- Stuffy nose
- Sneezing
- Sore throat
- Earache
- Malaise/tiredness
- Headache
- Muscle and/or joint ache
- Chilliness/Feverishness
- Cough
- Chest tightness
- Shortness of breath
- Wheeze

Additional to the categorical symptom diary card, a Visual Analogue Scale dairy card using a 100 mm scale, with the same symptoms, will be completed by the participants.

#### Participant cold perception questions

Two additional cold-related questions will be answered by the participant each morning. The first question asks whether the participant's perception of whether they have a cold or not, the second asks the participant's perception of improvement/worsening of the cold.

1. Do you have a cold: Yes/No

If the participant selects Yes to having a cold, then the second 7-point Likert scale "global change since yesterday" question is completed by the participant, as below:

- 2. Compared to yesterday, I feel that my cold is:
  - Very much better
  - Somewhat better
  - A little better
  - The same
  - A little worse
  - Somewhat worse
  - Very much worse

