Influenza A/California/2009 H1N1 virus infection and severe complications	Approximately 65% chance of becoming infected with Influenza A/California/2009 H1N1 virus (Sloan et al. 2020). Typical Influenza A/California/2009 H1N1 virus illness: abrupt onset of rhinitis, nasal stuffiness, fever, malaise, myalgia (muscle aches), and sore throat. Influenza, like many viruses, can cause more substantial health issues such as myocarditis (inflammation or damage to the heart muscle). However, the chance of this resulting in serious or permanent changes is rare, as most cases are minor and resolve without any lasting changes.	The safety profile of this batch of Influenza A/California/2009 H1N1 virus has been used for over 5 years by several groups globally. At hVIVO over 100 participants have been challenged with a different batch of Influenza A/California/2009 H1N1 virus. Influenza A/California/2009 H1N1 virus infection in healthy adults usually resolves without treatment within 3 to 7 days (Sloan et al. 2020). Strict inclusion and exclusion criteria will apply to ensure only healthy adults are enrolled in this study. There will be a daily medical monitoring in a Quarantine Unit for at least 8 days post-challenge. Qualified medical and nursing staff in the Quarantine Unit will monitor for and manage any symptoms. Participants will be closely followed up while being in quarantine. Electrocardiogram (ECG) will be performed, and cardiac enzymes will be tested at least 3 days, and 7 days post-viral challenge.
	Transient increase in alanine aminotransferase (ALT) or aspartate aminotransferase (AST) without clinical presentation, with a good prognosis upon improvement of infection.	ALT and AST will be monitored.
Transmission of Influenza A/California/2009 H1N1 virus to participants' close contacts	Influenza A/California/2009 H1N1 virus presence in nasal secretions can cause infection in close contacts.	Virus is usual absent from the nose by the time participants are discharged from quarantine. This will be confirmed by testing a nasal swab sample using by a qualitative virus antigen test or polymerase chain reaction (PCR) to determine

Potential Risk of Clinical Significance	Rationale for Risk	Mitigation Strategy						
		participants' suitability for departure.						
		In addition, participants will be instructed to avoid close contact with vulnerable people as described in Section 2.3.1.4 for two weeks after they leave the Quarantine Unit.						

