To evaluate the safety of SAB-176, when compared to placebo.	
 
Clinical symptoms.
 
Occurrence of unsolicited AEs from IV infusion up to Day 28 follow-up.
 
Occurrence of SAEs from IV infusion up to Day 28 follow-up.
 
	
To evaluate the safety of the Influenza A/California/2009 H1N1 virus challenge model.	
 
Occurrence of unsolicited AEs related to the viral challenge from viral challenge (Day 0) up to Day 28 follow up.
 
Occurrence of SAEs related to the viral challenge from viral challenge (Day 0) up to Day 28 follow up.
 
Use of concomitant medications from viral challenge (Day 0) up to Day 28 follow up.
 
	
Tertiary/Exploratory*		
To further explore the effect of SAB-176, in reducing the incidence of influenza illness due to Influenza A/California/2009 H1N1 virus, compared to placebo.	
 
Upper Respiratory Tract illness,
 
Lower Respiratory Tract illness,
 
Systemic Illness,
 
Febrile Illness,
 
Mild to moderate symptoms.
 
	
• To explore the Minimal Clinically Important Difference (MCID) in instrument change (e.g., symptom diary cards).	
 
The average amount of instrument-assessed change for all participants who rate themselves as "a little better" or "somewhat better.
 
Additional endpoints may be considered for this objective and added at a later stage.
 
	

Objectives	Endpoints
• To explore the effect of SAB-176, in reducing the incidence of infection due to Influenza A/California/2009 H1N1, virus compared to placebo.	
 
Influenza viral infection rates in upper respiratory samples by qRT-PCR and cell culture.
 

• To further explore the safety of the Influenza A/California/2009 H1N1 virus challenge model.	
 
Occurrence of haematological and biochemical laboratory abnormalities during the quarantine period.
 

• To explore the utility of wearable continuous monitoring for assessing Influenza A/California/2009 H1N1 virus infection/disease.	
 
Measures captured by continuous monitoring may be explored in relation to Influenza challenge.
 

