• To explore genomic, transcriptomic, and immunological markers of Influenza A/California/2009 H1N1 virus infection, as well as the effect of SAB-176.	
 
Blood and respiratory samples may be investigated to assess i) the host baseline status, ii) response to infection, and iii) impact on SAB-176, for example:         
 
Immune markers e.g., cytokines /
 
 
 

	
 
chemokines, immunoglobulins
 
Deoxyribonucleic acid (DNA) (e.g., single nucleotide polymorphisms [SNPs],
 

	
 
genome-wide association study [GWAS])
 
Ribonucleic acid (RNA) transcriptomics (e.g., RNA sequencing, microarray)
 

	This is a non-exhaustive list.

\*Note that tertiary objectives and endpoints are optional and might be assessed only if needed; therefore, not all tests might be performed and reported.

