## 9.4.6. Tertiary/exploratory Analysis

Except if otherwise specified, no formal statistical testing will be conducted for tertiary / exploratory endpoints. Only the descriptive statistics will be computed. These analyses will be described in the SAP.

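### The global-change question is not asked on the first morning without a cold, so the exploratory MCID estimate cannot include the final step out of illness

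*Combined protocol and SAP*

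**What the plan says.** Section 8.11, under the cold perception questions, opens without any condition: "Two additional cold-related questions will be answered by the participant each morning". The first question is whether the participant has a cold, Yes or No. The second is a seven-point rating of the cold against yesterday, and it carries a skip rule: "If the participant selects Yes to having a cold, then the second 7-point Likert scale" is completed. A No therefore ends the exchange for that morning.

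The rating serves as the anchor for one tertiary objective in Section 3, the Minimal Clinically Important Difference of instruments such as the symptom diary. The endpoint reads "The average amount of instrument-assessed change for all participants who rate themselves as" either a little better or somewhat better. The third improvement category, very much better, is not part of it. The same entry adds "Additional endpoints may be considered for this objective and added at a later stage".

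The status of the endpoint is modest. A footnote to Section 3 says "Note that tertiary objectives and endpoints are optional and might be assessed only if needed", and Section 9.4.6 says that, unless otherwise specified, "no formal statistical testing will be conducted for tertiary / exploratory endpoints". The detail is left to a SAP that Section 9.4.1 describes as still to be developed. Its text is not in the document supplied.

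**The concern.** An anchor-based MCID needs two things for each step: the change in the instrument and the participant's own rating of that change. The Schedule of Activities keeps the symptom diary going three times daily through Day 7 and once on Day 8, so the change in score is collected on the morning a cold is first denied. The rating is not.

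The gap comes from the questionnaire and is not ordinary missing data. It removes one kind of improvement, from having a cold to not having one, in everyone who makes that step. Going from slight residual symptoms to none is a change that a participant could well call a little better, which is what the endpoint is meant to measure. A rating that was never requested cannot be restored by an analysis rule or by an endpoint added later. What is at stake is how well the trial answers this exploratory objective.

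**Working it through.** The plan states no figure for the MCID estimate: no number of ratings, no number of contributing participants and no expected loss. There is nothing to reproduce, so the check sets the rule against the endpoint and then illustrates the size.

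**Rule against endpoint**

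| Yesterday | Today | Question 2 asked? | Can enter the MCID average? |
|---|---|---|---|
| Yes | Yes | Yes | Yes, if rated a little or somewhat better |
| Yes | No | No | No, whatever the rating would have been |
| No | No | No | No |

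The second row is the point. The first row matters too: a participant who later recovers still contributes every improving morning on which they reported a cold.

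**Share of improving steps left unrated**

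Assume one cold episode with k day-to-day improving steps, the last of them being the Yes-to-No step. Then k − 1 steps are rated and the unrated share is 1/k. The values of k are assumed; the documents give none.

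| k | Rated (k − 1) | Unrated share (1/k) |
|---|---|---|
| 1 | 0 | 100% |
| 2 | 1 | 50% |
| 3 | 2 | 33% |
| 4 | 3 | 25% |
| 6 | 5 | 17% |

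As a share of all improving steps in such a participant, 1/k is the most the endpoint can lose to the skip rule. Some final steps would have been rated very much better and so excluded in any case.

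**Does the step fall inside the observation window?**

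Table 1 says "Influenza A/California/2009 H1N1 virus infection in healthy adults usually resolves without treatment within 3 to 7 days". It does not say when the clock starts, and it describes infection, not the answer to the cold question. As an illustration, read it as illness lasting d = 3, 4, 5, 6 or 7 whole days, equally likely. With onset on day o, the first No morning is day o + d, and discharge is planned on Day 8.

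- Onset Day 0: o + d runs from 3 to 7; 5/5 = 100% by Day 8.
- Onset Day 1: 4 to 8; 5/5 = 100%.
- Onset Day 2: 5 to 9; 4/5 = 80%.
- Onset Day 3: 6 to 10; 3/5 = 60%.

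On these assumptions the unrated step occurs during quarantine for many, and possibly most, of those who report a cold.

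**How many participants?**

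Table 1 gives about a 65% chance of infection, so 0.65 × 60 = 39 expected infections. The documents do not say how many of those would answer Yes to having a cold, so 39 is not a count of affected participants.

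**The case against.** The skip rule has a sensible reason behind it. The item asks how my cold compares with yesterday, and that is awkward to put to someone who has just said they have no cold. Relaxing the rule without rewording the stem would produce a poorly posed question. This stands, and the fix has to deal with it.

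The endpoint is also optional, descriptive by default and open to extension, and no symptom scores are lost. That stands too and limits the importance of the point, although extending the endpoint later cannot supply a rating that was not asked for. The SAP may contain a scoring rule for these mornings; that cannot be checked here, and such a rule could only impute or exclude.

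Four stronger readings are tempting, and the documents do not support them.

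- A reader might infer that nearly every symptomatic participant is affected. The 65% refers to infections, and anyone still reporting a cold at discharge has no such step to lose. Section 1.1 itself allows for participants with clinically significant symptoms on Day 8.
- A reader might infer that the estimate comes only from people who stayed ill. It does not, since the earlier Yes mornings of those who recover can enter.
- A reader might infer that the MCID will be used to interpret recovery outcomes. No section applies it to any endpoint. The secondary symptom endpoints are the area under the symptom score curve, peak scores, Grade 2 or higher symptoms and symptomatic infection, and none is time to recovery.
- A reader might infer a bias of known direction. A share of unrated steps says nothing about whether those steps are larger or smaller than the rated ones.

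**Conclusion.** The point holds in a narrow form. The skip rule leaves the Yes-to-No morning without an anchor rating, so the exploratory MCID rests only on improvement reported while a cold is still present. This follows directly from Section 8.11 and the endpoint definition and needs no assumption.

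The size does rest on assumptions. The unrated step is 50%, 25% or 17% of improving steps for k = 2, 4 or 6, given one episode per participant and a transition that occurs in quarantine. These are ceilings on the loss to the endpoint as a share of all improving steps. The documents give neither the share of participants affected nor the effect on the estimated MCID. The endpoint wording also does not say whether the average is taken over participants or over rated mornings, so the weight of the missing step in the estimate is unknown.

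No primary, secondary or safety analysis is touched. This is a worthwhile small improvement to an optional endpoint and no threat to the trial's conclusions.

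**What to change.** In Section 8.11, ask question 2 when the participant answers Yes today or answered Yes the previous morning. Reword the stem so that it makes sense to someone who now has no cold, for example by asking how 'my cold symptoms' compare with yesterday.

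In the SAP, report the MCID both with and without these transition mornings, because it is debatable whether a step to no cold should be pooled with improvement during a cold. State at the same time whether the unit of the average is the participant or the rated morning.

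The cost is about one extra tick per cold episode and a small wording change on the paper diary card. The mornings rated now would still be rated. If the card can no longer be changed, the report should say that the MCID describes improvement only while a cold is still reported.
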